2.2 Secondary objectives

1. To compare the quantitative primary and secondary results of MagnetOsTM Granules to the results of Attrax® Putty from the AxA study (unpaired);
2. To investigate the relation between successful posterolateral fusion and interbody fusion, assessed at the one-year CT-scans used for the primary objective;
3. To compare the posterolateral spinal fusion rate of both MagnetOsTM Granules and autograft at one year with the fusion rates after two years, by using CT-scans;
4. To investigate the effect of blinding on perceived donor site pain, based on outcome measures reported by patients unblinded to the iliac crest donor site in comparison to these outcomes of the blinded patients from the AxA study;
5. To combine the study populations of the current study and the AxA study to investigate a) adjacent segment disease, in relation to length of construct and sagittal balance and b) risk factors for failures.

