Although iliac crest donor site morbidity is often reported by patients, the relevance of donor site pain is disputable when the bone is harvested via the same incision as used for the spinal fusion.³ The preliminary results of the AxA study indeed indicate that there is no relation between the real donor site and the iliac crest that is indicated by blinded patients. To determine if the often reported high incidence of donor site pain can be explained by the knowledge of the patient where the bone graft was taken, we will not blind the patients for the donor site in this study. The outcomes measures reported by patients unblinded to the iliac crest donor site will be compared to the outcomes of the blinded patients from the AxA study.

5. Combine the study populations of the current study and the AxA study

To combine the study data of both the current study and the AxA study will allow investigations on more infrequent phenomena on a relatively large population. Such a phenomenon is for example adjacent segment disease. This is a longterm complication where the adjacent joints and intervertebral disc may wear faster and cause degenerative disease. The occurrence of adjacent segment disease may be related to length of the construct and restoration of the sagittal balance. The occurrence of typical complications like infection and pseudoarthrosis can be related to risk factors like comorbidities, smoking, length of instrumented segment and so on.

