Adult patients qualifying for instrumented posterolateral spinal fusion of one to six levels in the thoracolumbar and lumbosacral region (T10-S2) with the use of autograft will be recruited by their treating orthopaedic surgeon or his/her assistant. After obtaining informed consent, they will be operated locally according to normal planning and the surgical techniques suggested in Appendix B. Per-operatively, after instrumentation of the spine and preparation of the bilateral trajectory for grafting, the randomized allocation of the graft type (left or right) will be disclosed. So in each patient, each side of the fusion trajectory will be one of the two conditions: the **autograft condition**, a combination of local bone obtained from decompression and/or preparation for fusion (facetectomy and denudement), supplemented with at least 50% corticocancellous bone harvested from the iliac crest, or the **MagnetOs condition**. Allocation of the conditions will always be to only one side of the spine, also when multiple levels are incorporated. Corticocancellous bone will be taken from only one iliac wing at the side of the autograft condition, unless this side is inappropriate due to previous harvesting or anatomical reasons. If possible, harvesting is done via the same posterior incision for spinal fusion. In case of an additional interbody fusion procedure, the cage is preferably filled with local autograft bone and positioned before opening of the randomization envelope. If the surgeon decides to use iliac crest bone for this device, the cage can only be inserted after the randomization and related harvesting side has been disclosed. All patients will be evaluated radiologically and clinically at several time points pre- and postoperatively (see Figure 3.1), and all (serious) adverse events that in any way may be related to the procedure will be carefully documented and evaluated to meet the objectives described in Chapter 2.

The expected duration of the study is approximately 4 years from the commencement of patient enrollment; enrollment is expected to take two years, followed by two years follow-up. After completion of one-year follow-up, the analysis for the primary outcomes will be done by the investigators at the UMC Utrecht.

[figure not shown]

Figure 3.1: Schematic overview of study design.

Rationale for intra-patient design

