7.2 Randomization, blinding and treatment allocation

Randomization for the allocation of the graft type will be performed with use of a computerized random-number algorithm. The randomization scheme will be maintained at the UMC Utrecht by the central principal investigator and study coordinator. The orthopaedic surgeon will be blinded to the allocation side of MagnetOsTM Granules, and thereby the contralateral allocation of autograft, as long as possible. He/she will receive an envelope containing the randomization of the patient which should be opened during surgery just

before the graft is needed (see suggested surgical technique, Appendix B). The iliac bone graft has to be taken from the same side where the autograft will be applied for posterolateral fusion according to the randomization. This will not be communicated to the patient. Whenever possible, bone harvesting will be done without making an additional skin incision.

In case an intra-operative decision is made to perform something different than what was intended for study enrollment, like for example to use local bone graft only or an uninstrumented spinal fusion, the patient will be considered a per-operative withdrawal and will not be treated with MagnetOs™ Granules. These patients will be replaced as described in paragraph 7.5.

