7.3.2 Surgical and postoperative procedures

Patients will be operated according to standard surgical procedures for instrumented posterolateral fusions between T10 and S2, with the only exception that one side of the spine will be grafted with the synthetic ceramic material MagnetOs™ Granules instead of bone harvested from the iliac crest. A recommended surgical technique is provided in Appendix B. In advance, the participating orthopaedic surgeons of each center will receive instructions on appropriate use of MagnetOs™ Granules from the principal investigator. Any questions that may arise concerning the surgical aspects of using MagnetOs™ Granules or autograft will be answered by the principal investigator.

Standard prophylactic antibiotics will be given for at least 24 hours, according the local surgical guidelines of each center. A thrombosis prophylaxis will be used according to the surgeons' preference. If preferred by the surgeon, patients will receive a restraining brace or orthosis postoperatively in order to protect the spine from (excessive) movements. Mobilization will be encouraged on the first postoperative day; physiotherapy will be offered during hospitalization and ambulatory if indicated.

According to standard care, standing anteroposterior and lateral radiographs will be taken postoperatively during hospitalization.

During surgery and hospital admission, the following information will be collected (CRF B):

- Date of surgery
- Surgeon's name
- Surgical technique
 - Instrumented spinal levels
 - Levels of decompression
 - Performance of vertebral osteotomy
 - Use of interbody device
 - Insertion side of TLIF
 - Additional surgical procedures
- With the use of a 20ml syringe an estimation of the volumes (in mL) of:
 - 1) obtained local bone and 2) obtained iliac crest bone and 3) the ratio of local bone / iliac crest bone used for posterolateral fusion
 - Local bone (or mixed autograft) applied per level for interbody fusion
 - (Mixed) autograft used per posterolateral fusion level

- Estimation of volume of MagnetOsTM Granules per posterolateral fusion level (in cc)
- Iliac crest side used for bone harvesting (right/left)
- Iliac bone harvested via same incision (yes/no)
- Additional time required for bone graft harvesting (minutes)
- Allocation of MagnetOsTM Granules (left/right)
- Surgical time (skin to skin and total anaesthesia time (begin and end of sedation)
- Estimated blood loss (cc)
- Use of vancomycine powder

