9.3 Analysis of secondary outcomes

1. To compare the quantitative primary and secondary results of MagnetOs™ Granules to Attrax® Putty a McNemar's test will be used as well as the mentioned GEE model;
2. As mentioned for the primary analysis, the odds-ratios and 95% confidence intervals for fusion rates of MagnetOs™ Granules and autograft will be calculated by using the GEE model. This model also allows to assess the effect of an additional interbody fusion;
3. For the comparison of the fusion rate after two years, the same method as for the primary efficacy analysis will be used;
4. VAS pain scores will be analyzed using the paired t-test, or Wilcoxon signed rank test in case of not-normally distributed data. To investigate the effect of blinding on perceived donor site pain, pain scores reported by the patients of this study and the AxA study will be compared using the unpaired t-test or Mann-Whitney U test.
5. To investigate risk factors of both study populations regression analysis will be done.

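### The donor-site pain comparison with AxA (secondary objective 4) ignores harvest route, so separate skin incisions, if any occur, could confound or dilute the estimated effect of knowing the donor side

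*Combined protocol and SAP*

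**What the plan says.** Section 2.2, objective 4, compares donor-site pain reported by patients of this study, who know the donor site, "in comparison to these outcomes of the blinded patients from the AxA study". Section 2.3, item 4, starts from the premise that "the relevance of donor site pain is disputable when the bone is harvested via the same incision as used for the spinal fusion". To test whether knowledge explains the reported pain, it states that "we will not blind the patients for the donor site in this study". It continues: "The outcomes measures reported by patients unblinded to the iliac crest donor site will be compared" with those of the blinded AxA patients.

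Same-incision harvest is a preference, not a requirement. Section 3: "If possible, harvesting is done via the same posterior incision for spinal fusion". Section 7.2: "Whenever possible, bone harvesting will be done without making an additional skin incision". Appendix B, step 8, likewise prefers that no second skin incision be made. Section 7.3.2 has the route recorded on CRF B, as the item "Iliac bone harvested via same incision (yes/no").

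The analysis in section 9.3, item 4, is that "pain scores reported by the patients of this study and the AxA study will be compared using the unpaired t-test or Mann-Whitney U test". It mentions no restriction, stratification or adjustment by harvest route.

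Section 7.2 also says that the harvest side, which follows the randomized autograft side, is not disclosed to the patient.

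**The concern.** The contrast is meant to isolate one thing: whether the patient knows which crest was used. Harvest route can disturb it in two ways.

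- **Extra wound.** A separate incision over the crest can hurt for reasons unrelated to knowledge. If the share of such patients differs between the studies, part of the difference in pain reflects incision type. The two studies ran at different times and patients were not randomized between them, so nothing in the design balances those shares.
- **Unmasking.** A patient with a scar over one crest can work out the donor side. In AxA, such a patient could be counted as blinded without being so. This mechanism matters only for AxA, because patients here are intended to know the side.

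At stake is the interpretation of one named secondary objective. A diluted result would understate the role of knowledge, and a confounded one could credit wound pain to it.

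**Working it through.** **No figure to reproduce.** The plan gives no sample size, effect size, standard deviation or power for objective 4, and no share of separate incisions for either study. What follows shows direction and sensitivity only.

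**Model.** Let δ be the effect on the pain score of knowing the donor side, w the extra pain from a separate wound, and fM and fA the separate-incision shares in this study and in AxA. Suppose all patients here know the side, and in AxA only those with a separate scar do. With μ the mean pain of a blinded same-incision patient:

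- mean here = μ + δ + fM·w
- mean in AxA = μ + fA·(δ + w)
- expected difference = (1 − fA)·δ + (fM − fA)·w

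This equals δ if neither study has separate incisions, or if the two disturbances happen to cancel.

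**Illustration, assuming δ = 10 and w = 10 points on a 100 mm VAS.**

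| fM | fA | Calculation | Estimate (true 10) |
|---|---|---|---|
| 10% | 10% | 0.9×10 + 0×10 | 9 |
| 20% | 20% | 0.8×10 + 0×10 | 8 |
| 10% | 0% | 1.0×10 + 0.1×10 | 11 |
| 20% | 0% | 1.0×10 + 0.2×10 | 12 |
| 0% | 10% | 0.9×10 − 0.1×10 | 8 |
| 0% | 20% | 0.8×10 − 0.2×10 | 6 |

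With equal shares q the estimate is (1 − q)·δ, so it is 10% too small at q = 10% and 30% too small at q = 30%. The wound term alone, with shares 15 points apart and w = 10 to 20 mm, is 0.15×10 = 1.5 mm to 0.15×20 = 3.0 mm.

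**Effect of restricting to same-incision patients.** Both disturbances vanish under the model and the estimate is δ. For precision, assume 100 patients per group, two-sided alpha 0.05, equal shares in both studies, and a standardized effect giving 80% power without separate incisions: (1.960 + 0.842)×√(2/100) = 0.396.

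| Share in both studies | Power, all patients (100 per group, effect × (1 − q)) | Power, same-incision only (100 × (1 − q) per group, full effect) |
|---|---|---|
| 5% | 0.759 | 0.780 |
| 10% | 0.713 | 0.757 |
| 20% | 0.611 | 0.707 |
| 30% | 0.500 | 0.650 |

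In these scenarios the undiluted effect outweighs the loss of patients.

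**Dependence on section 7.2.** The model assumes that patients here know the donor side. Suppose instead that section 7.2 is followed and same-incision patients here do not know it. The restricted comparison then sets blinded against blinded patients, with expected difference 0. The all-patient comparison gives (fM − fA)·(δ + w), which reflects incision route only. Neither estimates δ.

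**The case against.** Several objections have force.

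- **Inclusion is not shown.** A reader might infer that the comparison demonstrably contains separate-incision patients from both studies. The documents do not support that. They permit separate incisions here without saying that any occur. Section 9.3 names a test without defining its population. Sections 2.2 and 2.3 describe the comparator as blinded AxA patients, which could be read as leaving out anyone unmasked by a scar. This stands. Under that reading the dilution disappears, but the wound term remains: with fA = 0 the estimate is δ + fM·w.
- **AxA cannot be inspected.** Its harvest rule, CRF and handling of such cases are not in the documents. Section 2.3, item 1, calls the designs the same, yet donor-site blinding is known to differ, so that statement does not settle the harvest rule. This stands.
- **The effect may be small.** With 100 per group and an assumed VAS standard deviation of 20 to 30 mm, the standard error of the difference is 20×√0.02 = 2.8 mm to 30×√0.02 = 4.2 mm. A shift of 1.5 to 3 mm is then about 0.35 to 1.06 standard errors. With equal shares the bias is toward zero and cannot create a false effect. Both points are fair and limit the weight of the concern.
- **Restriction narrows the question.** The aim in section 2.3 is worded more broadly than its premise, and route is chosen during surgery, so restriction selects on a surgical variable. This is a good reason to keep the all-patient analysis alongside.
- **Other differences between the studies remain.** True, but this one is foreseeable and, in this study, already recorded.

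**Conclusion.** The point holds as a gap in the analysis of one secondary objective. The premise is framed for same-incision harvest, the protocol allows another route and records it, and the planned comparison does not use the record. If separate incisions occur, the extra wound can confound the contrast, and AxA patients with a separate scar may dilute it.

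The direction depends on the shares in the two studies, and the size cannot be derived from the documents. Every share, wound effect, knowledge effect and standard deviation used above is an assumption, so the figures should not be read as estimates of actual bias. Nor should it be inferred that primary efficacy or safety is touched: neither uses this contrast.

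The disagreement between section 7.2 and sections 2.2 and 2.3 on whether patients learn the donor side comes first. Until it is resolved, the contrast is not defined, and restricting by route could leave nothing to estimate.

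**What to change.** 1. Reconcile section 7.2 with sections 2.2 and 2.3 on whether patients in this study learn the donor side, and state in section 9.3, item 4, what the comparison assumes.
2. In section 9.3, item 4, and section 2.3, item 4, define the main blinding comparison as patients of both studies whose iliac bone was harvested through the fusion incision, using the CRF B item here and its counterpart in AxA.
3. Report the number excluded in each study and describe separate-incision patients apart. Keep the all-patient comparison as a sensitivity analysis.
4. Check whether AxA recorded the route. If it did not, report this study's pain results by route and state the limitation.

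The cost is a few sentences in the plan, a check of AxA data and slightly fewer patients in this one comparison. No new data are needed in this study. Recovering the route for AxA from operative reports could take more effort: section 11.1 limits source access in this study to local teams, the monitor and the inspectorate, and whether AxA had the same rule is not stated.

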3. STUDY DESIGN

This study is a multicenter, observer blinded, randomized, intra-patient controlled, non-inferiority trial with intra-patient comparisons, which is initiated and will be coordinated by the department of Orthopaedics from the UMC Utrecht, the Netherlands. A multicenter design is necessary to include the required number of patients (n=100) in an acceptable and feasible timeframe. Due to the experience with the AxA trial we have an established cooperation with the other centers which will make implementation in all centers relatively easy.

Adult patients qualifying for instrumented posterolateral spinal fusion of one to six levels in the thoracolumbar and lumbosacral region (T10-S2) with the use of autograft will be recruited by their treating orthopaedic surgeon or his/her assistant. After obtaining informed consent, they will be operated locally according to normal planning and the surgical techniques suggested in Appendix B. Per-operatively, after instrumentation of the spine and preparation of the bilateral trajectory for grafting, the randomized allocation of the graft type (left or right) will be disclosed. So in each patient, each side of the fusion trajectory will be one of the two conditions: the **autograft condition**, a combination of local bone obtained from decompression and/or preparation for fusion (facetectomy and denudement), supplemented with at least 50% corticocancellous bone harvested from the iliac crest, or the **MagnetOs condition**. Allocation of the conditions will always be to only one side of the spine, also when multiple levels are incorporated. Corticocancellous bone will be taken from only one iliac wing at the side of the autograft condition, unless this side is inappropriate due to previous harvesting or anatomical reasons. If possible, harvesting is done via the same posterior incision for spinal fusion. In case of an additional interbody fusion procedure, the cage is preferably filled with local autograft bone and positioned before opening of the randomization envelope. If the surgeon decides to use iliac crest bone for this device, the cage can only be inserted after the randomization and related harvesting side has been disclosed. All patients will be evaluated radiologically and clinically at several time points pre- and postoperatively (see Figure 3.1), and all (serious) adverse events that in any way may be related to the procedure will be carefully documented and evaluated to meet the objectives described in Chapter 2.

The expected duration of the study is approximately 4 years from the commencement of patient enrollment; enrollment is expected to take two years, followed by two years follow-up. After completion of one-year follow-up, the analysis for the primary outcomes will be done by the investigators at the UMC Utrecht.

[figure not shown]

Figure 3.1: Schematic overview of study design.

Rationale for intra-patient design

To investigate the efficacy of a bone graft substitute like MagnetOs™ Granules in the patient group that will benefit most from it, is challenging as these patients and surgeries are quite unique. The types of fusion in terms of location and number are highly variable and difficult to compare. Also, several surgical techniques are applied in addition to the posterolateral fusion at various levels. For example, posterior lumbar interbody fusion (PLIF) or transforaminal lumbar interbody fusion (TLIF). The solution to these impediments is to use a model where the patient is its own control. This is a recognized option in posterolateral spinal fusion investigations, because the right and left side of the spine are subject to similar procedures but physically separated.^{29,30} Moreover, the assessment of spinal fusion in terms of bone continuity and bone volume of both sides can be done independently. By using an intra-patient comparison model, the number of patients required for sufficient study power will be even less than half the number needed for traditional inter-patient comparisons. This is

because inter-patient variability of confounders for bony fusion is irrelevant with this approach. Finally, an important ethical advantage of this model is that the patient always receives the gold standard treatment for posterolateral fusion at one side of the spine, and for interbody fusion as well when an additional PLIF or TLIF procedure is performed. When the bone graft substitute would unexpectedly fail to establish a bony fusion, the implications will be much less severe because the contralateral side will have the gold standard treatment and a unilateral fusion of the spine is sufficient.

A frequently mentioned disadvantage of an intra-patient comparison model can be a disturbing effect of one condition on the other.³¹ This is definitely a concern when the stabilizing effect of fusion on one side of the spine might affect the other side. However, when spinal instrumentation is used, motion is drastically limited and not likely to be a factor of importance. Another disadvantage of an intra-patient model is when bioactive factors like BMPs are used, as these may influence the contralateral site. However, this is not a concern in the case of the current ceramic material, as it does not contain any bioactive additives. The main concern with the intra-patient model is that it does not allow assessment of the clinical effect of the intervention. This is a very important limitation that should be recognized. However, it is not an issue with respect to our research questions. The clinical outcome of spinal fusion is a matter on itself, which actually does not really reflect the functional and radiological presence of fusion especially not in the first years.³² Therefore, this study aims to evaluate the efficacy of in terms of percentage bony fusion, assessed at one year CT-scans.

